7. DISCONTINUATION FROM STUDY TREATMENT AND SUBJECT DISCONTINUATION/WITHDRAWAL

7.1. Discontinuation of Study Treatment

Subjects who discontinue from study treatment or withdraw from the study for any reason after the Day 1 dosing will be encouraged to complete the remaining study visits and evaluations and provide any additional follow-up information as required by the study, unless the subject specifically indicates that they will not participate in any further evaluations. The date of, and reason for, study treatment discontinuation will be recorded.

Permanent study treatment discontinuation is required for the following:

- The subject becomes pregnant during the active treatment phase of the study (Day 1 through Day 43).

Discontinuation of study treatment for abnormal liver function should be considered by the investigator when a subject meets one of the conditions outlined in Section 10.6.

If a clinically significant cardiac finding is identified (including but not limited to changes from baseline in corrected QT interval [QTc]) after the start of study treatment, the investigator or a qualified designee will determine if the subject can continue in the study and if any change in management is needed.

Subjects who discontinue from study treatment at any time after the first dose of study drug will not be replaced.

7.2. Subject Withdrawal from the Study

Subjects may withdraw from the study at any time at their own request, or may be withdrawn at any time at the discretion of the investigator for safety, behavioral, compliance, or administrative reasons. The date of and reason for withdrawal from the study will be recorded.

If the subject withdraws consent for disclosure of future information, the sponsor may retain and continue to use any data collected before such withdrawal of consent. If a subject withdraws from the study, the subject may request destruction of any samples taken and not yet tested. The investigator must document this in the site study records.

A subject may be withdrawn from the study for the following medical or administrative reasons:

- Withdrawal by subject (reason must be specified).
- An AE.
- Death.
- A protocol violation (reason must be specified, for example: lack of compliance, use of a prohibited concomitant medication, etc).
- The subject was lost to follow-up.
- Other reasons (reason must be specified, for example: the subject moved, pregnancy, investigator decision, sponsor decision to terminate trial, etc).

If a subject discontinues from the study, all Early Termination procedures should be conducted as detailed in the Schedule of Activities. The date a subject discontinues and the reason for discontinuation will be recorded in the source documentation and the electronic case report form (eCRF). If, however, a subject withdraws consent, no additional procedures are required except the collection of AE information. This information should be recorded in the source documentation and the eCRF.

Subjects who have been withdrawn from the study at any time after the first dose of study drug will not be replaced.

7.3. Lost to Follow-up

A subject will be considered lost to follow-up if the subject repeatedly fails to return for scheduled visits and is unable to be contacted by the study site.

The following actions must be taken if a subject fails to return for a required study visit:

- The site must attempt to contact the subject and reschedule the missed visit as soon as possible and counsel the subject on the importance of maintaining the assigned visit schedule and to ascertain whether or not the subject wishes to and/or should continue in the study.
- Before a subject is deemed lost to follow-up, the investigator or designee must make every effort to regain contact with the subject (where possible, 3 telephone calls, and if necessary, a certified letter to the subject's last known mailing address; or local equivalent methods). These attempts will be documented.
- Should the subject continue to be unreachable, the subject will be considered to have withdrawn from the study.

Subjects who have been lost to follow-up at any time after the first dose of study drug will not be replaced.

8. STUDY ASSESSMENTS AND PROCEDURES

Study procedures and their timing are summarized in the Schedule of Activities (Section 1.2). Adherence to the study design requirements, including those specified in the Schedule of Activities, is essential and required for study conduct. Protocol waivers or exemptions are not allowed. The details of activities outlined in the Clinical Operations Manual must be followed or will result in a protocol deviation.

Urgent safety concerns should be discussed with the sponsor immediately upon occurrence or awareness to determine if the subject should continue study treatment and/or be withdrawn from the study.

All screening evaluations must be completed and reviewed to confirm that potential subjects meet all eligibility criteria. The investigator will maintain a screening log to record details of all subjects screened and to confirm eligibility or record reasons for screen failure, as applicable.

Procedures conducted as part of the subject's routine clinical management and obtained before signing of the informed consent form (ICF) may be utilized for screening or baseline purposes provided the procedures met the protocol-specified criteria and were performed within the time frame defined in the Schedule of Activities.

8.1. Eligibility Confirmation

All subjects will have eligibility photographs of the mid-back to mid-thigh taken during screening that will be submitted to a sponsor designated reviewer to confirm eligibility. For these eligibility confirmation photographs the subject will be standing in a consistent, standardized relaxed standing pose (ie, standing position with relaxed gluteus muscles) and will be wearing a standardized photographic garment. Specific instructions for taking the eligibility confirmation

photographs as well as for providing them to, and receiving confirmation (or lack thereof) from, the sponsor designated reviewer will be provided in the Clinical Operations Manual.

Only subjects deemed eligible for the study by sponsor designated reviewer will be allowed to receive study treatment. Subjects deemed ineligible by the sponsor designated reviewer will be considered screen failures.

All photographs from this study are the property of Endo and de-identified images may be utilized for clinical development, scientific communication, marketing, regulatory purposes, and/or legal applications as required/desired by Endo.

8.2. Efficacy Assessments

Efficacy assessments will be evaluated at times specified in the Schedule of Activities. Below is a general description of each of these assessments. Specific instructions and questionnaires/forms (where appropriate) will be provided in the Study Operations Manual. Due to the potential of bias, virtual efficacy assessments (Body-Q Appraisal of Cellulite, Body Dysmorphic Disorder Questionnaire, CR-PCSS-Buttock, I-GAIS, [REDACTED] and [REDACTED] are not allowed.

8.2.1. Imaging for Outcome Assessments

Although digital photographs are not direct efficacy measurements, digital photography will be utilized in the assessment of certain efficacy measurements (ie, to assess certain cellulite severity parameters at specific intervals). At screening, the investigator or qualified designee will photograph each of the 2 treatment areas (both buttocks and both thighs) independently using a sponsor-supplied standardized digital camera in a standardized manner. For subsequent visits only the areas receiving treatment (both buttocks or both thighs) will be photographed. The subject will be standing in a consistent, relaxed standing pose (ie, standing position with relaxed gluteus muscles) for each photography session and will be wearing a standardized photographic garment as described in the Photography Manual. These photographs will be taken before and after marking of the treatment area for dosing at treatment visits.

All photographs from this study are the property of Endo and de-identified images may be utilized for clinical development, scientific communication, marketing, regulatory purposes, and/or legal applications as required/desired by Endo.

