6.5. Measures to Minimize Bias

This is an open-label, nonrandomized study; measures to minimize bias using treatment blinding or randomization are not applicable to this study.

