9. STATISTICAL CONSIDERATIONS AND METHODS

9.1. Sample Size Determination

The proposed sample size is 150 subjects (70 buttocks subjects and 80 thigh subjects). The sample size is based on the rate of I-GAIS responders defined as subjects with an I-GAIS rating of "Improved", "Much Improved", or "Very Much Improved" on Day 90.

The sample size calculation was based on the following assumptions: 1) the proportion of 1-level I-GAIS responders is 70% for buttocks and 60% for thighs (based on results from earlier studies of CCH in EFP), 2) the estimated proportion of 1-level I-GAIS responders in this study will be no less than 60% for buttocks and 50% for thighs with a 95% chance, and 3) the dropout rate will be approximately 10%.

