Fitzpatrick skin type	X					
Hexsel CSS Subsection D ^b	X					
Vital signs	X	X ^c	X ^c	X ^c	X	X
ECG	X					
Hematology, chemistry, and urinalysis	X				X	X
Serum pregnancy test	X					
Urine pregnancy test		X	X	X	X	X
Immunogenicity sample collection		X			X	X
Body-Q Appraisal of Cellulite ^d	X				X	X
Body Dysmorphic Disorder Questionnaire						X
Imaging for eligibility confirmation	X					

Table 2: Schedule of Activities (Continued)

Procedure	Screening (Day-28 to Day -1)	Day 1 (Treatment Session I)	Day 22 (+7 days) (Treatment Session II)	Day 43 (+14 days) (Treatment Session III)	Day 90 (+14 days)	Day 180 (+14 days)/ Early Termination
Eligibility confirmation ^e	X					
Selection of treatment region (both buttocks or both thighs)	X					
Imaging for outcome evaluations (IntelliStudio) ^f	X	X	X	X	X	X
Ultrasound ^g		X	X	X	X	X
CR-PCSS ^h	X	X	X	X	X	X
I-GAIS ⁱ			X	X	X	X
Select and mark up to 12 target dimples for CCH injection in each treatment area (each buttock or each thigh)		X	X	X		
[REDACTED]		X	X	X	X	X
Study drug administration		X	X ^j	X ^j		
[REDACTED]				X		
[REDACTED]					X	
Concomitant medications	X	X	X	X	X	X
Injection site reactions/local tolerability in areas treated		X	X	X	X	X
All other AEs ^k	Monitored throughout the study					

^a Performed prior to any study-required assessments, unless exceptions granted for standard of care procedures.

^b Should be reassessed and verified prior to dosing. In the event that any safety laboratory testing results are unavailable prior to the subject's first dosing visit, the investigator will notify the sponsor to discuss on a case-by-case basis, prior to administering any study treatment to the subject.

^c Vital signs will be collected up to 4 hours prior to, and at 15 and 30 minutes after, study treatment administration on Days 1, 22, and 43.

^d Assessment should be completed independently of, and prior to, any investigator cellulite assessments (CR-PCSS, I-GAIS, [REDACTED]).

^e Provided by an evaluator designated by the sponsor.

^f Before and after marking target dimples at treatment visits. No manipulation of the treatment area should be done prior to the "before" images.

^g Performed at selected site(s) only.

^h CR-PCSS-Buttock and CR-PCSS-Thigh will both be done at screening. Thereafter, only buttock treated subjects will be assessed by CR-PCSS-Buttock.

ⁱ I-GAIS will be completed after CR-PCSS when both are required at the same visit.

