3.7.4. Clinician Reported Photonumeric Cellulite Severity Scale (CR-PCSS) - Buttock

The CR-PCSS - Buttock (Table 5) will be used to assess the severity of cellulite of both buttocks (each buttock, independently).

The CR-PCSS - Buttock is a 5-level photonumeric scale developed specifically for clinicians and used by the Investigator to assess the severity of the subject’s cellulite in each buttock by live assessments at Screening, Day 1, Day 22, Day 43, Day 90, and Day 180 Visits.

The ratings range from 0 (None) to 4 (Severe) with labels and descriptors to aid the Investigator in the assessments. This assessment should be made while the subject is in the standing position with relaxed gluteus muscles.

Table 5: CR-PCSS -Buttock

Rating	Level of Severity	Description
0	None	No dimples or evident cellulite
1	Almost None	Few dimples that are mostly superficial in depth
2	Mild	Several dimples of which most are shallow in depth
3	Moderate	Many dimples of which most are moderate in depth
4	Severe	A lot of dimples with some of more severe depth

Investigators who are physicians will be trained and qualified on the use of the CR-PCSS-Buttock prior to assessing any subjects.

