4.6.1.3. One-Level I-GAIS Responder for Either Buttock or Either Thigh

One-level I-GAIS Responder for either buttock is defined as any buttock-treated subject with an improved (+1, +2 or +3) score on the I-GAIS for at least one buttock at an evaluation visit.

One-level I-GAIS Responder for either thigh is defined as any thigh-treated subject with an improved (+1, +2 or +3) score on I-GAIS for at least one thigh at an evaluation visit.

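### Pre-treatment images and CR-PCSS-Buttock ratings are collected twice, but the legible plan uses neither pair to gauge I-GAIS scoring without drug or to separate pre-treatment shift from change after CCH

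*Protocol*

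**What the plan says.** **Design and primary result.** The study is open-label, nonrandomized and single-arm within each cohort. Protocol 6.5 says "measures to minimize bias using treatment blinding or randomization are not applicable to this study". The primary endpoint is the proportion of subjects scored +1 or better on the I-GAIS at Day 90. A thigh subject counts as a responder on an improved "score on I-GAIS for at least one thigh at an evaluation visit" (SAP 4.6.1.3), and the buttock rule is parallel. SAP 7.7.1.1 reports this proportion with a Wilson 95% interval.

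**Images.** Protocol 8.2.1: "At screening, the investigator or qualified designee will photograph each of the 2 treatment areas (both buttocks and both thighs) independently". Later sessions photograph only the treated region, with the same pose and garment requirements. The SAP schedule (Table 2) marks outcome imaging at both Screening and Day 1, and its footnote requires a set before marking at treatment visits. Screening to Day 1 may not exceed 28 days (Protocol 5.4).

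**I-GAIS.** Protocol 8.2.2.5 and SAP 3.7.7 compare the Day 1 pretreatment image with the images at Days 22, 43, 90 and 180. The only legible analysis output for the photographs themselves is a listing (SAP 7.7.4).

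**CR-PCSS-Buttock.** SAP 3.7.4 has it rated "by live assessments at Screening, Day 1, Day 22, Day 43, Day 90, and Day 180 Visits". SAP 4.6.2.1 and the dedicated row of SAP Table 18 set baseline at Screening. The general baseline row of Table 18 uses the last non-missing value before first dose. SAP 7.7.2.2 summarizes observed values and change at Days 22, 43, 90 and 180 only.

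**The concern.** In a single-arm study with an unmasked physician rating, part of any responder rate is photographic and rating variation. The plan states no untreated or placebo I-GAIS rate, so the reader of the results cannot judge how large that part is. Yet two standardized, unmarked image sets of the treated region exist before any injection, and no legible section rates one against the other.

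The CR-PCSS-Buttock issue is more concrete. Two pre-treatment ratings exist, the earlier one is the baseline, and the later one enters no summary. Whatever happened between Screening and Day 1 is then carried into the reported change at every post-treatment visit. At stake is how far the two investigator-rated scales can be read as the effect of CCH.

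**Working it through.** **1. The plan's own figure.** Protocol 9.1 assumes "the proportion of 1-level I-GAIS responders is 70% for buttocks and 60% for thighs" and that the estimate "will be no less than 60% for buttocks and 50% for thighs with a 95% chance", with 10% dropout from 70 buttock and 80 thigh subjects. Evaluable n is 70 × 0.9 = 63 and 80 × 0.9 = 72.

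P(observed ≥ L) = Φ((p − L)/√(p(1 − p)/n))

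- Buttock: √(0.70 × 0.30/63) = 0.0577; 0.10/0.0577 = 1.73; probability 95.8% (exact binomial 96.3%).
- Thigh: √(0.60 × 0.40/72) = 0.0577; 1.73; 95.8% (exact 96.7%).

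The stated 95% reproduces. It is a statement of sampling precision around rates from earlier CCH studies, and no no-drug rate enters it.

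**2. CR-PCSS-Buttock baseline.** For each buttock and visit v:

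(v − Screening) = (v − Day 1) + (Day 1 − Screening)

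The last term is pre-treatment and is the same at every visit. Inclusion criterion 2a requires a score of 2 or 3 at Screening and on Day 1 (only 2b is limited to Screening). Among eligible dosed buttock subjects the term is therefore −1, 0 or +1. If a fraction d moves from 3 to 2 and a fraction u from 2 to 3, the reported mean change moves by u − d at all visits. For example, a net 10% moving from 3 to 2 contributes 0.10 × (−1) = −0.10. The documents give neither d nor u, so neither size nor direction is known.

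**3. I-GAIS: from per-area to either-area.** Assumptions, not in the documents: per-area false +1 rate p of 5%, 10% or 20%, and left-right correlation r of 0 or 0.5.

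Either-area rate f = 2p − [p² + r·p(1 − p)]

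**4. Contribution to an observed 60%.** Let t be the proportion truly improved, with false positives arising only in the rest. Then 0.60 = t + (1 − t)f, so t = (0.60 − f)/(1 − f), and the contribution is 0.60 − t = 0.40f/(1 − f).

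| p | r | f | f/p | Points of an observed 60% |
|---|---|---|---|---|
| 0.05 | 0.5 | 0.074 | 1.48 | 3.2 |
| 0.05 | 0 | 0.098 | 1.95 | 4.3 |
| 0.10 | 0.5 | 0.145 | 1.45 | 6.8 |
| 0.10 | 0 | 0.190 | 1.90 | 9.4 |
| 0.20 | 0.5 | 0.280 | 1.40 | 15.6 |
| 0.20 | 0 | 0.360 | 1.80 | 22.5 |

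**5. Would a Screening/Day 1 reading be informative?** Wilson 95% intervals with all dosed subjects read:

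- Background 10%: 7/70 gives 4.9% to 19.2%; 8/80 gives 5.2% to 18.5%.
- Background 20%: 14/70 gives 12.3% to 30.8%; 16/80 gives 12.7% to 30.0%.

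That is enough to tell a small background from a large one. It is not enough for a fine correction.

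**The case against.** **Purpose.** Protocol 4.2 calls the study exploratory. The analysis is descriptive, with no null rate, success threshold or planned claim over a control. This stands: the gap limits interpretation and invalidates no test.

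**Bias control.** A reader might infer that Protocol 6.5 dismisses bias control altogether. It does not: it rules out only blinding and randomization. The plan standardizes camera, pose and garment, places CR-PCSS before I-GAIS, has subject assessments done first and alone, and bars virtual efficacy ratings. These steps reduce bias but do not measure the residual +1 rate.

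**Either-area rule.** A reader might say that it doubles false positives. Under the assumptions above the multiplier is 1.4 to 1.95, and doubling is only approached when the two sides are nearly independent. SAP 7.7.1.1 and 7.7.2.1 also already report each treatment area.

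**Size.** Subtracting f directly would suggest that 7 to 36 points of an observed 60% are background. That ignores false positives falling on subjects who would be responders anyway. Setting the result against the 10-point gap between 60% and 50% is also unsound, because that gap is a sampling margin. The assumed 5% to 20% has no source in the documents, and SAP Table 8 anchors +1 at an obvious improvement.

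**What the pair can show.** Screening/Day 1 is not a no-treatment control. It spans at most 28 days and reflects rating and photographic noise, not 90-day change. The CR-PCSS table is constrained because eligibility holds both ratings to 2 or 3, so it understates variability. Both limits stand.

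**Redaction.** Exploratory objectives and several assessment and analysis sections are blacked out. The absence of a comparison can be asserted only for the legible text, which does include the I-GAIS definition and schedule and the primary and secondary analyses.

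**Conclusion.** The point holds in limited form. For CR-PCSS-Buttock it follows from the SAP's definitions alone: baseline is Screening, Day 1 is rated but not summarized, and any pre-treatment shift is therefore reported as change after CCH. The shift is at most one level per buttock in either direction among eligible dosed subjects, and its mean is unknown. The Screening row in Table 18 can be read as a deliberate exception to the general baseline rule, but no reason is given.

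For I-GAIS, the legible plan has no estimate of +1 scoring without drug. On assumed per-area rates of 5% to 20% and left-right correlation of 0 to 0.5, background would supply about 3 to 22.5 points of an observed 60%. The documents do not support saying that the responder rate is inflated by any particular amount, or that the primary analysis is invalid.

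**What to change.** **Free, recommended.** In SAP 7.7.2.2, add the Screening-to-Day 1 change in CR-PCSS-Buttock for each buttock. Show change from the Day 1 pre-dose rating beside change from Screening at Days 22, 43, 90 and 180. Reconcile SAP 4.6.2.1 and the CR-PCSS row of Table 18 with the general baseline rule, or state why Screening is used. Add a footnote that eligibility limits both ratings to 2 or 3, so the table understates variability. This needs no new data.

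**Optional, small cost.** Leave the primary I-GAIS rating as it is; Protocol 2.1 reports 121 subjects already dosed by 13 April 2020, so changing it would be disruptive. As a supplementary reading from stored unmarked images, have the same physicians rate Screening/Day 1 pairs mixed with Day 1/Day 90 pairs. Hide the visit labels and use the earlier image of each pair as the reference. Report per-area and either-area +1 proportions with Wilson 95% intervals by cohort.

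The cost is up to 150 subjects × 2 areas × 2 pairs = 600 comparisons plus a masked reading procedure, with no new visits or images. Raters may sometimes guess which pair contains Day 90, and the report should say that the result describes rating and photographic noise over at most 28 days.

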8.2.2. Subject and Investigator Cellulite Assessments

Investigator cellulite assessments are independent of the subject assessments. Therefore, all subject cellulite assessments must be completed before the investigator's cellulite assessments are initiated. Subject assessments will occur while the subject is alone with no study site personnel in the room. Investigators will be instructed not to verbalize their ratings while in the presence of the subject and vice versa.

8.2.2.1. Body-Q Appraisal of Cellulite

The Body-Q Appraisal of Cellulite is a subset of questions from the Body-Q questionnaire that was developed to measure patient perceptions of weight loss and/or body contouring (Scott et al, 2012).

8.2.2.2. Clinician-reported Photonumeric Cellulite Severity Scale - Buttock

The CR-PCSS-Buttock will be used to assess the severity of cellulite of both treatment areas (each buttock, independently). The CR-PCSS-Buttock is a 5-level photonumeric scale developed specifically for clinicians and used by the investigator to assess the severity of the subject's cellulite in each buttock by live assessments. The ratings range from 0 (None) to 4 (Severe) with labels and descriptors to aid the investigator in the assessments. This assessment should be made while the subject is in the standing position with relaxed gluteus muscles.

Investigators who are physicians will be trained and qualified on the use of the CR-PCSS-Buttock prior to assessing any subjects.

